6. METHODS AND ASSESSMENTS

2 arms: phacoemulsification alone and phacoemulsification and iStent to compare the results of both arms in terms of IOP at one year.

No film or video taping will be used for this study.

6.1. Randomisation and Blinding

This section should describe randomisation and blinding procedures (if applicable to the

study design). Include a description or a table that describes how study subjects will be assigned to the study groups. The timing and procedures for planned and unplanned breaking of randomization codes should be included. Include statement when unmasking may occur and who may unmask.

Randomised controlled study. 1:1 ratio allocation 32 patients 16 phacoemulsification alone 16 phacoemulsification with iStent Randomisation by shuffled envelope system.

Follow up will be at 1 day, 1 week, 1 month, 3 months, 6 months, 1 year after surgery.

Patient will be blinded to the procedure.

The IOP measure and reader will be blinded to the procedure.

There will be no planned breaking of randomisation.

Unplanned breaking will happen if any envelopes are damaged or lost.

Unmasking will take place after 1 year post operation by the study team to inform the patient of the procedure.

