4. TRIAL SCHEDULE

Part of research Schedule:

Patients who meet the inclusion criteria will be invited to participate in this study. Patient will be randomly assigned to either phacoemulsification alone, or phacoemulsification with iStent by random envelope shuffle technique.

After operation the patient will be followed up at day 1, week 1, week 2, months 1, 3, 6 and 12.

At each visit the patient will have the following tests: Tonometry (IOP check) - Not to be taken by the operating surgeon, to be taken by 2 people, one IOP checker and one reader.

Part of Standard of Care:

At each visit:

Visual Acuity, Slit lamp examination and Fundoscopy.

At 6 monthly intervals:

Visual field examination

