5. STUDY DESIGN

Single centre, randomised prospective trial, the patient and the IOP checking staff will be blinded. Randomised by random envelope shuffle technique.

1:1 ratio allocation

2 arms: phacoemulsification alone and phacoemulsification and iStent.

16 patients in each arm, 32 patients in total.

The post-operative management is the same for both arms

After operation the patient will be followed up at day 1, week 1, week 2, months 1, 3, 6 and 12.

At each visit the patient will have the following tests: Tonometry (IOP check) - Not to be taken by the operating surgeon, to be taken by 2 people, one IOP checker and one reader.

The target IOP is 18mmHg for patients with PAC or mild PACG. If the IOP rises above 18mmHg in 2 consecutive visits then the original glaucoma medication(s) will be reinstated or as per the clinicians discretion.

IOP at 12 months will be the primary outcome measure. The target pressure will be based on the Asia Pacific Glaucoma Guidelines. For PAC with high IOP and PAS and early PACG, the target will be $>/=20\%$ from base line or 18mmHg whichever is lower. b. The Asia Pacific Glaucoma Guidelines classifies “PAC with High IOP and PAS” to be “glaucoma with moderate 5-year risk for visual loss” and to treat the IOP with a target of $>/=20\%$ or 18mmHg whichever is lower.

The target IOP is 18mmHg for patients with PAC or mild PACG. If the IOP rises above 18mmHg in 2 consecutive visits then the original glaucoma medication(s) will be reinstated or as per the clinicians discretion.

The patient will be masked to the treatment arm given, but the investigators will not be masked.

The procedure will be performed by 2 surgeons: [name] and [name], the follow up visits and monitoring of pressure will be done by the investigation team.

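### Allocation is by shuffled envelopes with no held list or concealment safeguard described, and a damaged or lost envelope triggers breaking of the randomisation

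*Protocol*

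**What the plan says.** Section 4 assigns patients "by random envelope shuffle technique". Sections 5, 5.1 and 6.3 repeat the method, and Section 6.1 puts it as "Randomisation by shuffled envelope system". The ratio is 1:1, 16 patients per arm and 32 in all. Nothing in these sections says who prepares or holds the envelopes, whether they are numbered, sealed or opaque, when one is opened, or whether openings are logged.

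On code breaking, Section 6.1 says "There will be no planned breaking of randomisation" and then "Unplanned breaking will happen if any envelopes are damaged or lost". Its retained template text asks for more: "The timing and procedures for planned and unplanned breaking of randomization codes should be included". A separate sentence in Section 6.1 places unmasking of the patient after the one-year visit, and Section 6.3 adds that patients who withdraw are unmasked.

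On masking, Section 5 says the patient is masked, "but the investigators will not be masked". The staff who measure and read IOP are masked (Sections 6.1 and 8.5). Section 5.1 relies on the randomisation to prevent surgical bias.

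**The concern.** Randomisation protects the comparison only if the person enrolling can neither foresee nor choose the next allocation. The protocol fixes a method that, as described, has no reference list behind it. It then fixes a response to a handling accident that opens up the randomisation. With a held list, a damaged or lost envelope would simply be reissued and nothing would need to be broken.

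What is at stake is selection at enrolment. Patients are identified in clinic with no formal screening visit (Section 6.3), and the investigators learn each arm once it is given. Masked tonometry protects the reading of IOP. It does nothing about which patient enters which arm. In a trial of 32, a few allocations influenced by knowledge of what comes next could unbalance the arms, and no audit trail is described that would show or rebut this.

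This is trial conduct and belongs in the protocol; it is not a detail normally left to a statistical analysis plan.

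**Working it through.** **1. The plan's own figure.** Section 11.1 gives a difference of 2.6 mmHg, SD 2.4, alpha 0.05 and power 0.80. Taking the test as two-sided (the protocol does not say; one-sided would give 11):

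n per arm = 2 × (1.960 + 0.842)² × (2.4/2.6)² = 2 × 7.849 × 0.852 = 13.38, rounded up to 14. The stated 14 is reproduced, and 16 per arm are planned.

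**2. Does losing one envelope matter for power?** Two-sided t-test at the same planning values:
- 16 v 16: noncentrality 2.6 / (2.4 × √(1/16 + 1/16)) = 3.06 on 30 df, power 84.2%.
- 16 v 15: noncentrality 2.6 / (2.4 × √(1/16 + 1/15)) = 3.01 on 29 df, power 83.0%.

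The loss is 1.2 percentage points, so the issue is not power.

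**3. What recovering a lost envelope requires.** Assume one pack of 16 + 16. Suppose k patients have been allocated, a of them to the stent arm, and then one unused envelope is lost. That leaves 31 − k envelopes. If they hold 16 − a stent allocations, the lost one was phacoemulsification alone; if they hold 15 − a, it was a stent allocation. Unless one arm is already complete, settling this at the time of the loss means opening envelopes until one arm is fully accounted for, up to all 31 − k:

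| Patients already allocated (k) | Envelopes that may have to be opened |
|---|---|
| 0 | 31 |
| 10 | 21 |
| 20 | 11 |

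If the opened envelopes keep their order, future allocations are disclosed to whoever opens them. If they are reshuffled, the remaining sequence is redrawn mid-trial. The other course is to leave the arm unknown until the pack is used up; the protocol does not choose it. With a held list, the number opened is 0.

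**4. What the protocol asks for against what it supplies.** The template in Section 6.1 wants the timing and procedure of any unplanned breaking and who may unmask. The answer on unplanned breaking is one sentence giving the trigger. It does not say what is broken, who does it, how it is recorded, or how the next patient is allocated.

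**5. A figure that should not be counted.** For one 16/16 pack with past allocations known, let g(a, b) be the expected number of correct guesses by someone who always guesses the arm with more envelopes left:

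g(a, b) = max(a, b)/(a + b) + [a/(a + b)]·g(a − 1, b) + [b/(a + b)]·g(a, b − 1)

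g(16, 16) = 19.07, and 19.07/32 = 59.6%. This follows from the fixed 16/16 total. A listed 16/16 sequence has the same value, so it measures neither the harm of shuffling nor the gain from a list.

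**The case against.** The other side has good points, and four stronger readings that a reader might infer do not stand.

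- *The rule unmasks patients.* Section 6.1 treats breaking and unmasking in separate sentences, and an unused envelope belongs to no patient. Breaking could mean that the pack is opened, counted, restored and reshuffled. Unmasking of treated patients is not shown.
- *The missing arm can never be known.* It can, because the total is fixed at 16/16 and past allocations are known to the investigators; recovering it may be what the rule is for. What remains is the price of recovery at that moment, which is opening the rest of the pack.
- *The sequence cannot be audited.* That is an inference from silence. Envelopes can be sealed and numbered after a shuffle, and the protocol does not say they are not. The supportable statement is that no audit trail is described.
- *The bias can be given in mmHg or as an inflated type I error.* Guessing from a depleting pack is equally possible under a listed 16/16 sequence. Larger figures need perfect foresight and deliberate steering, and the protocol supplies neither.

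It is also fair to say that a surgeon cannot be masked to a stent being implanted, that a well-shuffled sealed pack is as unforeseeable as a list, and that the primary reading is taken by masked staff. Being unmasked to past arms is not the same as foreseeing the next one. All of this stands, but it leaves untouched the stated rule on damage or loss and the absence of any described safeguard on who handles the envelopes.

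**Conclusion.** The point holds as a weakness in allocation concealment. A shuffle with no described backup list, joined to a rule that breaks the randomisation when an envelope is damaged or lost, exposes or disturbs future allocations in a 32-patient trial whose investigators are not masked. It should be corrected before enrolment. It does not by itself invalidate the design.

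The size cannot be stated as a bias. What can be stated is that up to 31 − k unopened allocations are put at risk by a loss after k patients, while the effect on power is negligible. This assumes a single pack of 32 and that no list or log exists beyond what the protocol describes. If such safeguards are in use, the remaining defect is that the protocol omits them and carries a rule that would then be unnecessary.

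**What to change.** In Sections 4, 5, 5.1, 6.1 and 6.3, replace the shuffle with a computer-generated 1:1 list, prepared and held by a named existing staff member who neither recruits nor operates. Use sequentially numbered, opaque, sealed envelopes, each opened only after consent and baseline data are logged, with the opening recorded.

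In Section 6.1, replace the damaged-or-lost sentence with a rule that the envelope is reissued from the held list and the event logged, without revealing any other allocation. Do not simply delete the sentence, since the section would then say nothing on unplanned breaking. State separately who may unmask a patient and when, bringing together what Sections 6.1 and 6.3 already say.

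The cost is a few hours of set-up and some protocol wording. The one real demand is to find a list holder. The protocol names nobody for this, and data management sits with the principal investigator and co-investigators (Section 10.1). The sample size does not change. The predictability that comes with a fixed 16/16 total remains.

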6.2. Contraception and Pregnancy Testing

For females of childbearing age will be asked if they are pregnant.

6.3. Study Visits and Procedures

Provide a brief outline of the all the study visits, procedures to be done during the study, follow up after the study and discontinuation visit.

a. Screening Visits and Procedures

No formal screening visit.

The patient will be identified in clinic and be invited to participate in the trial.

b. Study Visits and Procedures

Patients who meet the inclusion criteria will be invited to participate in this study. Patient will be randomly assigned to either phacoemulsification alone or phacoemulsification with iStent by random envelope shuffle technique.

After operation the patient will be followed up at day 1, week 1, week 2, month 1, months 3, 6 and 12.

At each visit the patient will have the following tests: Tonometry (IOP check) - Not to be taken by the operating surgeon, to be taken by 2 people, one IOP checker and one reader.

c. Final Study Visit:

Final visit will be at 1 year after surgery.

Patient will be informed of the procedure performed.

They will resume normal follow up in the clinic for their glaucoma.

d. Post Study Follow up and Procedures

At each visit the patient will have the following tests: Tonometry (IOP check) - Not to be taken by the operating surgeon, to be taken by 2 people, one IOP checker and one reader.

As part of their routine assessment they will be examined for evidence of complications related to the operation.

e. Discontinuation Visit and Procedures

Subjects may withdraw voluntarily from participation in the study at any time.

They will be unmasked regarding the procedure performed. They will need to continue to have the same follow up schedule because it is the same standard of care, except that at each visit they will have tonometry taken by the same doctor (instead of a two person technique) in the clinic who will not be blinded to their operation status.

Subjects may also withdraw voluntarily from receiving the study intervention for any reason. If the patient does not have the operation, then they will receive the standard management for their condition which is usually 6 monthly follow up if their condition is stable.

7. TRIAL MATERIALS

iStent is a micro-bypass stent made of titanium that is FDA and HSA approved. It is inserted into the Schlemm's canal to by pass the trabecular meshwork to improve outflow of aqueous eye fluid and lower IOP.

The control arm is phacoemulsification, which is an operation that removes the lens of the eye and replaces it with a intra ocular lens. It is the standard of care for cataracts but not standard of care for primary angle closure and primary angle closure glaucoma. However, phacoemulsification has been shown to have a beneficial effect on the drainage angle and IOP in primary angle closure and primary angle closure glaucoma.

7.1. Trial Product (s)

The iStent is a micro-bypass stent made of titanium and is inert inside the eye. The istent is designed to stay in the eye and does not need to be removed.

Here are the reported complications related to iStent insertion:

- Stent occlusion
- Hyphaema
- IOP elevation more than 10mmHg
- Stent malposition
- Subconjunctival haemorrhage
- iritis

7.2. Storage and Drug Accountability

iStent needs to be stored in room temperature.

8. TREATMENT

8.1. Rationale for Selection of Dose

NA

8.2. Study Drug Formulations

NA

8.3. Study Drug Administration

NA

8.4. Specific Restrictions / Requirements

NA

8.5. Blinding

Patient will be blinded to the procedure.

The IOP measure and reader will be blinded to the procedure.

8.6. Concomitant therapy

NA

9. SAFETY MEASUREMENTS

9.1. Definitions

Reporting procedures for:

- Deaths and life threatening events
- other SAEs: Hospitalisation events.
- Other adverse events

Standard procedures for reporting adverse events

Information regarding adverse events (including incidence, duration, seriousness, severity, relationship to treatment and action taken) will be recorded throughout the one year of the study. If adverse events occur, the first concern will be the safety of the study participants.

9.2. Collecting, Recording and Reporting of “Unanticipated Problems Involving Risk to Subjects or Others” – UPIRTSO events to the NHG Domain Specific Review Boards (DSRB)

An adverse event is defined as any untoward medical occurrence in a patient administered a therapeutic treatment and that does not necessarily have a causal relationship with this

treatment. An adverse event (AE) can therefore also be any unfavourable and unintended sign (including an abnormal laboratory finding), symptom, or disease temporally associated with the use of a therapeutic treatment, whether or not related to the therapeutic treatment.

Any adverse event is to be recorded on the appropriate case report form. These will be graded by an Investigator at each site for severity and relationship to study treatment. The severity should be completed using the following definitions as guidelines:

Mild: Awareness of sign or symptom, but easily tolerated.

Moderate: Discomfort enough to cause interference with usual activity.

Severe: Incapacitating with inability to work or do usual activity.

Not applicable: In some cases, an adverse event may be an 'all or nothing' finding which cannot be graded.

To determine the relationship (if any) between an adverse event and the study drug a causal relationship is deemed present if a determination is made that there is a reasonable possibility that the adverse event may have been caused by the drug.

All adverse events that are therapy related and unexpected should also be reported to the Institutional Review Board.

Procedure for reporting Serious Adverse Events

A Serious Adverse Event is defined as any adverse event occurring that results in any of the following outcomes: death, a life-threatening adverse event, inpatient hospitalization or prolongation of existing hospitalization, a persistent or significant disability/incapacity, or a congenital anomaly/birth defect. Important medical events that may not result in death, be life threatening, or require hospitalization may be considered a serious adverse event when, based upon appropriate medical judgment, they may jeopardize the patient or subject and may require medical or surgical intervention to prevent one of the outcomes listed in this definition. All serious adverse events should be reported to the Institutional Review Board.

9.3. Collecting, Recording and Reporting of Serious Adverse Events (SAEs) to the Health Science Authority (HSA)

Reporting of adverse events involves the Principal Investigator submitting to the approving CIRB the completed SAE Reporting Form within the stipulated timeframe. The Principal Investigator is responsible for informing the institution representatives or regulatory bodies as required and appropriate.

"A serious adverse event or serious adverse drug reaction is any untoward medical occurrence at any dose that:

- Results in death.
- Is life-threatening (immediate risk of death).
- Requires inpatient hospitalization or prolongation of existing hospitalization.

- Results in persistent or significant disability/incapacity.
- Results in congenital anomaly/birth defect.
- Is a Medically important event.

Medical and scientific judgment should be exercised in determining whether an event is an important medical event. An important medical event may not be immediately life threatening and/or result in death or hospitalization. However, if it is determined that the event may jeopardize the subject and/or may require intervention to prevent one of the other adverse event outcomes, the important medical event should be reported as serious.”

All SAEs that are unexpected and related to the study device will be reported. The investigator is responsible for informing HSA no later than 15 calendar days after first knowledge that the case qualifies for expedited reporting. Follow-information will be actively sought and submitted as it becomes available. For fatal or life-threatening cases, HSA will be notified as soon as possible but no later than 7 calendar days after first knowledge that a case qualifies, followed by a complete report within 8 additional calendar days.

9.4. Safety Monitoring Plan

Safety monitor is [name] – Senior Consultant in Ophthalmology, Khoo Teck Puat Hospital

9.5. Complaint Handling –

Complaints will be handled by the principal investigator

9.6. Potential Risks

The potential risks to the patient specific to the iStent are:

The iStent has risks of IOP spikes, infection, bleeding in the anterior chamber and iStent dislocation.

The potential risks to the patient specific to the phacoemulsification are:

Infection, bleeding, reduced vision, inflammation, posterior capsular rupture, vitreous loss, retinal detachment, endophthalmitis, suprachoroidal haemorrhage and IOL dislocation.

10. DATA ANALYSIS

10.1. Data Quality Assurance

Data management will be handled by the principal investigator and co-investigators. Patient data obtained for this study will be entered in electronic format. Accuracy checked will be performed by the investigators who will be cleaning the data entered from time to time.

10.2. Data Entry and Storage

Research data will be stored on a laptop that is password encrypted and locked to a desk in a

secure office in Khoo Teck Puat Hospital.

11. SAMPLE SIZE AND STATISTICAL METHODS

11.1. Determination of Sample Size

Details on sample size calculation and the means by which data will be analysed and interpreted.

In particular, specify all of the following:

- Null Hypothesis
Phacoemulsification with micro-bypass stent has no difference in effect on IOP compared to phacoemulsification alone in primary angle closure and primary angle closure glaucoma at 1 year after surgery.
- Alternate hypothesis
Phacoemulsification with micro-bypass stent has a better IOP lowering effect compared to phacoemulsification alone in primary angle closure and primary angle closure glaucoma at 1 year after surgery.
- Type I error rate = 0.05
- Type II error rate = 0.2

Sample Size Calculation:

Based on published data of phaco and phaco iStent RCT in open angle glaucoma:

Mean IOP for control at 1 year (phaco only group) – 19.2mmHg +/- 3.1

Mean IOP for combined group at 1 year (phaco+istent group) – 16.6mmHg +/-3.5

Alpha = 0.05

Power = 0.80

SD: 2.4

Difference: 2.6

Sample size = 14 in each arm

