Phacoemulsification alone reduces the IOP in the first year, but tends to return to baseline after 1-2 years. A meta-analysis comparing phacoemulsification with phacoemulsification with iStent found it to be in favour to the phacoemulsification with iStent group (SMD=-0.46). There have been 4 randomised controlled trials comparing phacoemulsification with phacoemulsification + iStent in primary open angle glaucoma and 6 studies evaluating phacoemulsification + iStent again in open angle glaucoma. The four randomised controlled trials showed the phaco+iStent group to have a greater IOP reduction. (17% vs 9%, 27% vs 16%, 10% vs 8%, 8% vs 5%)

There have been no studies evaluating phacoemulsification + iStent in primary angle closure

or primary angle closure glaucoma.

This study will be the first randomised controlled trial in primary angle closure or primary angle closure glaucoma. This will also be the first iStent trial in Singapore on Singaporeans.

This is important because primary angle closure is much more common in the Singaporean Chinese population and the most common cause of irreversible bilateral blindness in the Asia. Phacoemulsification has become a more common procedure to help manage this condition although trabeculectomy or combined phacotrabeculectomy is still the gold standard surgery. Phacoemulsification with iStent may be a suitable operation for this condition that can avoid the higher risks of the trabeculectomy and yet have a better IOP control than phacoemulsification alone.

b. Rationale for Doses Selected

Phacoemulsification with 1 iStent will be used because in the open angle studies, it had a improved IOP control compared to phacoemulsification alone. 2 iStents or 3 iStents can be inserted and have been reported to have good response, but with very limited data to show any added benefit given the additional cost.

c. Rationale for Study Population

The patients will be selected from the clinic patient population. Primary angle closure and primary angle closure glaucoma have been chosen because the disease is more relevant and common in the Singaporean context compared to the western countries. Also this disease has not been studied using the iStent.

d. Rationale for Study Design

Randomised controlled trial with blinding to the patient and the IOP measurer and reader with adequate sample size to compare both groups is the best way to answer our research question.

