3. STUDY POPULATION

3.1. List the number of subjects to be enrolled.

All patients will be recruited from the ophthalmology and visual science department of Khoo Teck Puat Hospital. There will be no restriction on race. Children will be excluded from this study as the surgeons have limited experience operating on children.

The project aims to recruit 32 patients, 16 in each arm of the randomisation, of phacoemulsification alone and phacoemulsification and iStent Implant.

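### The sample size uses an SD of 2.4 mmHg, below both SDs cited beside it (3.1 and 3.5); on those SDs, power for 2.6 mmHg is about 52% at 14 per arm and 58% at 16, not 80%.

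*Protocol*

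**What the plan says.** Protocol section 11.1 sets "Type I error rate = 0.05", a type II error rate of 0.2 and power of 0.80. It bases the calculation on a published trial in open-angle glaucoma. The control arm is given as "Mean IOP for control at 1 year (phaco only group) – 19.2mmHg +/- 3.1", and the phaco plus iStent arm as 16.6 mmHg with an SD of 3.5. It then lists an SD of 2.4 and a difference of 2.6, and ends with "Sample size = 14 in each arm". It gives no origin for the 2.4.

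Enrolment is set elsewhere. Section 3.1 states: "The project aims to recruit 32 patients, 16 in each arm of the randomisation". Sections 5, 5.1 and 6.1 repeat 16 per arm. No power is stated for 16.

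Section 11.2 plans independent t-tests between the groups at 12 months and mentions no baseline adjustment. Section 5 makes IOP at 12 months the primary outcome measure, and section 2.3(a) names mean IOP at 1 year as one of two primary outcomes.

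**The concern.** The 2.6 mmHg difference is the gap between the two cited means, so the effect comes from the published trial. The variability does not: 2.4 is smaller than either SD reported for the same arms. Required sample size grows with the square of the SD, so this one input roughly halves the number of patients.

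At stake is the type II error that the protocol promises. Section 1.2(d) describes the sample size as adequate, and section 1.2(a) presents the study as the first randomised trial of this device in angle closure. If the real chance of missing the planned effect is about twice the stated one, a non-significant result would say much less about absence of benefit than a reader of section 11.1 would assume.

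**Working it through.** **Inputs (section 11.1 unless noted).** Control 19.2, SD 3.1; combined arm 16.6, SD 3.5; difference 19.2 − 16.6 = 2.6; SD used 2.4; alpha 0.05; power 0.80; 1:1 allocation (section 5); 16 per arm planned (section 3.1); independent t-test (section 11.2). Sidedness is not stated. Two-sided is the main case because it reproduces the protocol's figure; one-sided is shown because the alternative is worded directionally ("Phacoemulsification with micro-bypass stent has a better IOP lowering effect compared to phacoemulsification alone").

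**1. Reproduce the stated figure.** Normal approximation:

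n per arm = 2 × (1.960 + 0.842)² × (SD / difference)²

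SD 2.4: 2 × 2.802² × (2.4/2.6)² = 15.70 × 0.852 = 13.4, rounded up to **14**. This matches. (The exact t-test version gives 15; one-sided versions give 11 or 12.) So 2.4 is the value actually used.

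**2. SD implied by the cited arms.**

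Pooled SD = √((3.1² + 3.5²)/2) = √((9.61 + 12.25)/2) = √10.93 = **3.31**

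Any pooled or weighted average lies between 3.1 and 3.5, so 2.4 cannot be one.

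**3. Same formula with 3.31.** 15.70 × (3.306/2.6)² = 15.70 × 1.617 = 25.4, i.e. **26 per arm**; the exact t-test needs **27**.

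**4. Power for 2.6 mmHg.** Noncentral t with 2n − 2 degrees of freedom and noncentrality 2.6 / (SD × √(2/n)). For SD 3.306 and n = 16 this is 2.6 / (3.306 × 0.3536) = 2.22.

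| SD | 14 per arm, two-sided | 16 per arm, two-sided | 16 per arm, one-sided | n per arm for 80%, two-sided |
|---|---|---|---|---|
| 2.4 (as used) | 78.8% | 84.2% | 91.1% | 15 |
| 3.1 | 57.0% | 63.2% | 75.0% | 24 |
| 3.31 (pooled) | **51.7%** | **57.6%** | 70.2% | **27** |
| 3.5 | 47.3% | 52.9% | 65.9% | 30 |

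The normal approximation gives slightly higher values at the pooled SD: 54.8% at 14 and 60.4% at 16. A simulation with unequal SDs of 3.1 and 3.5 (200,000 replicates) gives 57.6% at 16 per arm with the pooled t-test and 57.4% with Welch's test.

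**5. What 16 per arm can deliver.** At SD 3.31, the difference detectable with 80% power is 3.4 mmHg, a standardised effect of 3.385/3.306 = 1.02. Conversely, 80% power for 2.6 mmHg needs an SD no larger than 2.6/1.02, about 2.54, which is below both cited SDs.

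**The case against.** The best defence of 2.4 is that it may be the SD of a change from baseline, or a residual SD after baseline adjustment. With equal SDs at both times and a correlation r between baseline and 12 months (an assumption; the protocol gives none), the change-score SD is 3.31 × √(2(1 − r)). This equals 2.4 at r of about 0.74. The adjusted SD, 3.31 × √(1 − r²), equals 2.4 at about 0.69. Neither correlation is absurd, and section 11.1 does speak of an IOP-lowering effect. But the protocol does not say that 2.4 arose this way. Its outcome is IOP at 12 months and its test is unadjusted, so such an SD would not fit the planned analysis.

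Three narrower points stand without changing the conclusion:

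- The stated 80% belongs to 14 per arm, not 16. The like-for-like comparison is therefore 52% against 80%; the two extra patients per arm raise it only to 58%.
- The sum itself is right. The fault lies in the input, not in the calculation.
- The cited SDs come from open-angle eyes, so 3.31 is itself uncertain for angle closure. It is nevertheless the only 12-month variability the protocol offers.

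The meta-analytic standardised difference of 0.46 in section 1.2(a) is also smaller than the implied 2.6/2.4 = 1.08. Its outcome and time point are not given, so nothing here rests on it.

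**Conclusion.** The concern holds. Section 11.1 takes its effect from the cited trial but uses an unsupported SD below both of that trial's SDs. On the protocol's own figures, the probability of missing a true 2.6 mmHg difference is about 48% at 14 per arm and 42% at 16, against the stated 20%. Neither the smaller cited SD nor a one-sided test restores 80%; both together give 75% at 16 per arm.

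This assumes an unadjusted two-sample t-test on 12-month IOP, equal allocation and all randomised patients analysed. The last assumption is generous: section 3.5 withdraws patients for surgical complications, failed stent insertion or by request, and section 3.6 allows no replacement. So 58% is an upper figure, and 52% applies if 14 per arm remain. The finding concerns mean IOP only, not the co-listed outcome of unmedicated IOP at or below 21 mmHg.

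**What to change.** If enrolment stays at 32, rewrite the calculation in section 11.1:

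- Replace the SD of 2.4 with the pooled 3.31 from the cited arms.
- Replace the lines giving power 0.80, type II error 0.2 and 14 per arm, which would otherwise contradict the new text.
- State that 16 per arm gives about 58% power for 2.6 mmHg, or 80% power for 3.4 mmHg, at two-sided 0.05 with all 32 patients analysed (about 52% for 2.6 mmHg if 14 per arm are evaluable).
- State that the result will be read from the estimated difference and its 95% confidence interval.
- Bring the claim of adequate sample size in section 1.2(d) into line.

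This costs wording only and needs no extra patients; the stated power becomes less favourable.

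There are two alternatives if the sponsor wants to keep the 80% claim. One is to give the source of 2.4 and plan the analysis it belongs to, such as a baseline-adjusted comparison. The other is to enrol 27 per arm, 54 in total rather than 32, before any allowance for withdrawals.
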